3.2 Participant Criteria

Inclusion Criteria

1) 18 - 90 years of age

2) Male or female

3) Planning to undergo total hip or knee arthroplasty, either primary or revision

4) Fluent in English

5) Willing and able to sign an informed consent form and HIPAA authorization and to comply with study procedures

Exclusion Criteria

1) Infectious disease within the last month

2) Immune-suppressant therapy within the last 2 months (e.g., azathioprine or cyclosporine)

3) Chronic medication with potential immune-modulatory effects (e.g., daily oral morphineequivalent intake > 30 mg)

4) Major surgery within the last 3 months or minor surgery within the last month.

5) History of substance abuse (e.g., alcoholism, drug dependency)

6) Pregnancy

7) Autoimmune disease interfering with data interpretation (e.g. lupus)

8) Renal, hepatic, cardiovascular, or respiratory diseases resulting in clinically relevant impaired function

9) Active malignancy

10) Participation in another clinical trial of an investigational drug or device within the last month that, in the investigator's opinion, would create an increased risk to the participant or compromise the integrity of the study

11) Other conditions compromising a participant's safety or the integrity of the study

12) Allergy to active ingredient of CocoaVia®, the study intervention.

13) Frequent consumption of dark chocolate and flavanol containing foods (e.g. black tea, red wine, apples)

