3.3 Enrollment

We plan to enroll 36 participants. All participants will be enrolled at Stanford Health Care.

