4.0 Materials and Methods

The proposed study is designed as a randomized, controlled, and double-blind study comparing a daily dose of cacao flavanol versus placebo. Cocoa flavanol is commercially available as a nutrient (CocoaVia®), manufactured by Mars Inc. CocoaVia® is supplied in 125 mg capsules

containing 15% epicatechin, the active anti-inflammatory ingredient. Based on our preliminary data a daily oral dose of 1,000 mg will be used in this study.

After participants have completed the informed consent process they will be randomized to one of two treatment groups - half to group A and half to group B. Group A participants will receive a daily oral dose of 1,000 mg cocoa flavanol (CocoaVia®) for 5 days before surgery, while group B participants will receive a daily oral dose of a placebo for 5 days before surgery.

Patients will be involved in study procedures from the time they consent to participate through postoperative week 6. Procedures to evaluate baseline condition, hospital course, and recovery will take place as follows:

Questionnaires: Before hospitalization participants will complete questionnaires to evaluate expectations prior to surgery (patient expectations), stress level (perceived stress scale), pain and function (WOMAC), anxiety (POMS-anxiety scale), and baseline fatigue and functional impairment (surgical recovery scale; SRS). Participants will complete SRS and WOMAC scales daily while they are in the hospital, and weekly following discharge to track recovery over a sixweek course.

Objective measures of function: Physical function will also be measured objectively by directly monitoring participant activity using a wearable device (ActiGraph) providing measurements for physical activity/function and sleep. Participants will be asked to wear the device beginning 1 week before surgery through postoperative week 6.

Blood draws: Blood will be drawn at 4 time points; once before administration of the study intervention (40ml), 1 hour before surgery (30ml), 1 hour after surgery (30ml), and on post-op day 1 (30ml). Blood will be processed for analysis of cell signaling with mass cytometry (NFkB in innate immune cells), HMGB1 plasma concentrations, and epicatechin (flavanol) plasma concentrations. Blood samples will be identified using a study code, and will be analyzed in labs at Stanford University and Stanford Health Care (Stanford Hospital).

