5.0 Statistical Measures

5.1 Outcome Measurements

The primary outcome is the cumulative NFkB signal in innate immune cells 1 and 24 hours after surgery.

Secondary outcomes include HMGB1 plasma levels, functional recovery trajectories (measured objectively with ActiGraph and subjectively with WOMAC function sub-scale), postoperative pain resolution (measured with WOMAC-pain subscale), and postoperative resolution of fatigue and resulting impairment of daily activities (measured with SRS). Trajectories will be reflected by the time to resolve function to mild impairment, the time to resolve pain to mild levels, and the time to resolve fatigue to 50% of maximum postoperative fatigue.

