5.2 Analysis Plan

Page 6 Protocol Version # 1 The primary outcome NFkB signaling in innate immune cells between the two study groups will be analyzed with a non-paired t-test. A similar exploratory analysis will be conducted for secondary outcomes. However, the study is powered to detect differences of the primary outcome.

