5.3 Sample size

Based on data from previous studies of surgical patients receiving an active (arginine nutritional supplement) versus a control treatment, it is reasonable to assume that intervention-related effect sizes (changes in signaling activity) are about twice as large as pooled standard deviations. This has been noted for signaling molecules downstream of TLR4 in response to arginine supplementation. TLR4-signaling (NFkB) is the primary outcome of this proof-of-concept study. A sample size of 16 patients per group should therefore provide ~80% at p<0.05 to detect an intervention-related group differences.

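### The primary t-test takes no account of hip versus knee or of revision status: it stays valid, but it may lose precision and leaves chance imbalance unadjusted, and a prespecified covariate would cure both at little cost

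*Combined protocol and SAP*

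**What the plan says.** Section 3.2 admits four kinds of operation: "Planning to undergo total hip or knee arthroplasty, either primary or revision". Section 3.3 sets the size: "We plan to enroll 36 participants". Section 4.0 says that participants are "randomized to one of two treatment groups - half to group A and half to group B"; it names no stratification factor, block or minimisation factor. The same section, under additional data, has details of the surgery recorded during hospitalisation, but no later section gives them a role in the analysis.

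Section 5.1 defines the endpoint: "The primary outcome is the cumulative NFkB signal in innate immune cells 1 and 24 hours after surgery". Section 5.2 fixes the comparison: the outcome "between the two study groups will be analyzed with a non-paired t-test". No covariate is named. Section 5.3 assumes effects that "are about twice as large as pooled standard deviations" and attaches about 80% power to 16 patients per group.

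**The concern.** Sections 1.0 and 2.0 present the HMGB1-NFkB axis as one switched on by tissue trauma. On that reasoning, the kind of operation is a plausible source of variation in the primary outcome. The preliminary data that link this signalling to recovery are described for hip replacement, so the documents do not show whether knees or revisions give the same level or spread.

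Two separate things follow if the joint matters:

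- **Precision.** Hip-knee variation enters the error term of an unadjusted t-test even when the arms are perfectly balanced on joint.
- **Chance imbalance.** With 36 patients and no balancing described, the arms can differ noticeably in their share of hips. The planned primary estimate does not adjust for that.

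**Working it through.** **Inputs from the protocol.** 36 participants (3.3); half to each arm, so 18:18 (4.0); 16 per group, 0.05 level and about 80% power (5.3); assumed effect about 2 pooled SDs (5.3). Sidedness is not stated; two-sided is assumed.

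**Inputs the protocol does not give.** The hip/knee mix, the primary/revision mix, and the hip-knee difference in NFkB. These are varied below.

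**1. The plan's own power figure.** Two-sided noncentral t with n = 16 per arm, 30 df and noncentrality d × √(n/2):

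- d = 2: power 99.98%.
- d = 1: power 78.1%.
- d = 1.02 (1.022 in the calculation): power 79.9%.

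The stated 80% therefore corresponds to an effect of about 1 SD, not 2 SD. That mismatch is a separate matter. It is used here only to fix the two effect sizes at which the loss should be read.

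**2. How often the arms differ by 4 or more hips.** With H hips among 36 and 18 per arm, the number of hips k in arm A is hypergeometric, and the arms differ by |2k − H|. For H = 18, a gap below 4 means k = 8, 9 or 10:

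P(gap < 4) = 0.2110 + 0.2605 + 0.2110 = 0.6825, so P(gap ≥ 4) = 0.3175.

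| Hips among 36 | P(gap ≥ 4) |
|---|---|
| 18 | 31.8% |
| 16 or 20 | 31.5% |
| 12 or 24 | 28.9% |
| 6 or 30 | 17.7% |
| 17 or 19 (gap must be odd, so 5 or more) | 18.1% |
| random count, 50% share | 24.3% |
| random count, 30% or 70% share | 20.1% |

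The 32% is the maximum under fixed 18:18 allocation. The low values for odd totals partly reflect the cut-off: at 17 or 19 hips a gap of 3 or more has probability 50.5%.

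**3. What such a gap does to the estimate.** With 18 per arm, a 4-hip gap shifts the arm difference by 4/18 = 0.22 of the hip-knee difference. For assumed differences of 0.5, 1.0 or 1.5 within-joint SD, the shift is 0.11, 0.22 or 0.33 SD.

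**4. What joint variation does to power.** With an even mix and a hip-knee difference of g within-joint SDs, the total SD is √(1 + g²/4). Power uses d divided by that factor, with 16 per arm.

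| g (assumed) | Total SD | Power, d = 1.02 | Power, d = 2 |
|---|---|---|---|
| 0 | 1.000 | 79.9% | 99.98% |
| 0.5 | 1.031 | 77.4% | 99.96% |
| 1.0 | 1.118 | 70.6% | 99.8% |
| 1.5 | 1.250 | 61.0% | 99.2% |

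At 18 per arm, with all 36 evaluable, the d = 1.02 column reads 84.6%, 82.4%, 75.9% and 66.4%.

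**5. What adjustment costs and returns.** With joint in the model and arms balanced, power at 16 per arm and d = 1.02 is 79.8% (29 df) for any g, and 79.7% with a second covariate (28 df). If joint is irrelevant, the price is thus 0.1 to 0.2 percentage points. With an 11:7 against 7:11 split of hips and knees, the arm-joint correlation is 4/18 = 0.222. Adjustment then multiplies the variance of the arm estimate by 1/(1 − 0.222²) = 1.05 and removes the shift in step 3 under an additive model.

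**The case against.** The strongest defence is that an unadjusted comparison in a single-centre, 36-patient proof-of-concept trial is a legitimate choice. Much of this stands:

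- A reader might infer that the primary comparison is biased or invalid. The documents do not support that. Patients are randomised, and the error rate of the t-test already allows for chance imbalance.
- A reader might infer that about a third of allocations will be unbalanced. That needs an even hip/knee split, which the protocol does not state; most other assumptions give less.
- A reader might infer that the trial is underpowered because of this. At the protocol's assumed 2 SD effect, power stays above 99% in every scenario shown. The loss is material only near 1 SD, and every loss figure rests on an assumed hip-knee difference.
- The pooled SD in section 5.3 may already contain variation between operations. If so, adjustment is a gain over the planned power rather than the repair of a loss.
- Because surgical details are recorded, an adjusted sensitivity analysis remains possible, and section 5.2 does not forbid one. Nor does silence in section 4.0 prove that the allocation list is unstratified.

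What does not stand is the idea that nothing should therefore change. Whatever the list looks like, the factor is absent from the planned primary analysis. Adjusting only after an imbalance has been seen would be post hoc, whereas naming the covariate now costs almost nothing.

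**Conclusion.** The point holds as one of precision and chance imbalance, not of validity. The plan mixes hip and knee, primary and revision operations, describes no balancing, and ignores both factors in the primary test although the data will be on file.

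A gap of 4 or more hips occurs in at most about 32% of 18:18 allocations, and in about 24% if the hip count is left to chance at a 50% share. The power cost at 16 per arm and a 1.02 SD effect is about 2, 9 or 19 percentage points for assumed hip-knee differences of 0.5, 1.0 or 1.5 within-joint SD with an even mix. It is below 1 point at a 2 SD effect. No size can be given for revision status, since the documents give neither the share of revisions nor their effect.

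The case for change rests on asymmetry: a negligible cost if joint is irrelevant, and a useful gain if it is not and the true effect is nearer 1 SD than 2.

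**What to change.** In section 5.2, before unblinding, replace the t-test as the primary analysis with a linear model of the cumulative NFkB signal on arm and joint (hip or knee). Add primary versus revision as a further covariate if enough revisions are enrolled, with the threshold for enough also fixed before unblinding. Report the adjusted arm difference with its 95% CI as the primary result, and keep the unadjusted t-test as a sensitivity analysis.

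The cost is a short addition to 5.2 and one or two degrees of freedom. No new data collection should be needed, provided that the recorded surgical details include joint and revision status.

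If allocation has not started, stratifying the list by joint with small permuted blocks is an optional addition. Blocks of 2 or 4 would cap the difference in hips between arms at 1 or 2. The cost is two lists instead of one, and up to half a block of imbalance within each joint. If allocation has started, the covariate alone is sufficient.

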3.3 Enrollment

We plan to enroll 36 participants. All participants will be enrolled at Stanford Health Care.

4.0 Materials and Methods

The proposed study is designed as a randomized, controlled, and double-blind study comparing a daily dose of cacao flavanol versus placebo. Cocoa flavanol is commercially available as a nutrient (CocoaVia®), manufactured by Mars Inc. CocoaVia® is supplied in 125 mg capsules

containing 15% epicatechin, the active anti-inflammatory ingredient. Based on our preliminary data a daily oral dose of 1,000 mg will be used in this study.

After participants have completed the informed consent process they will be randomized to one of two treatment groups - half to group A and half to group B. Group A participants will receive a daily oral dose of 1,000 mg cocoa flavanol (CocoaVia®) for 5 days before surgery, while group B participants will receive a daily oral dose of a placebo for 5 days before surgery.

Patients will be involved in study procedures from the time they consent to participate through postoperative week 6. Procedures to evaluate baseline condition, hospital course, and recovery will take place as follows:

Questionnaires: Before hospitalization participants will complete questionnaires to evaluate expectations prior to surgery (patient expectations), stress level (perceived stress scale), pain and function (WOMAC), anxiety (POMS-anxiety scale), and baseline fatigue and functional impairment (surgical recovery scale; SRS). Participants will complete SRS and WOMAC scales daily while they are in the hospital, and weekly following discharge to track recovery over a sixweek course.

Objective measures of function: Physical function will also be measured objectively by directly monitoring participant activity using a wearable device (ActiGraph) providing measurements for physical activity/function and sleep. Participants will be asked to wear the device beginning 1 week before surgery through postoperative week 6.

Blood draws: Blood will be drawn at 4 time points; once before administration of the study intervention (40ml), 1 hour before surgery (30ml), 1 hour after surgery (30ml), and on post-op day 1 (30ml). Blood will be processed for analysis of cell signaling with mass cytometry (NFkB in innate immune cells), HMGB1 plasma concentrations, and epicatechin (flavanol) plasma concentrations. Blood samples will be identified using a study code, and will be analyzed in labs at Stanford University and Stanford Health Care (Stanford Hospital).

Additional data to be collected will be demographic and socioeconomic information, medical history including co-morbidity prior to surgery, and recent medication history. During hospitalization opioid analgesic consumption, pain level, details of surgery and anesthesia, incidence of complications, and time to "discharge ready" will be recorded.

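### WOMAC and SRS switch from daily to weekly scoring at each patient's own discharge, so recorded times to resolution depend on length of stay and can understate an early recovery benefit

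*Combined protocol and SAP*

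**What the plan says.** The questionnaire paragraph of section 4.0 sets the schedule: "Participants will complete SRS and WOMAC scales daily while they are in the hospital, and weekly following discharge". Follow-up ends on a calendar counted from surgery: "Patients will be involved in study procedures from the time they consent to participate through postoperative week 6".

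Section 5.1 turns the scores into secondary outcomes: "Trajectories will be reflected by the time to resolve function to mild impairment, the time to resolve pain to mild levels", together with "the time to resolve fatigue to 50% of maximum postoperative fatigue". Section 5.2 says that the primary outcome "will be analyzed with a non-paired t-test" and adds: "A similar exploratory analysis will be conducted for secondary outcomes".

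The documents give no common post-operative days for the questionnaires, no visit windows, no rule for dating a resolution that falls between two forms, no interval-censored method and no adjustment for length of stay. The activity monitor, by contrast, runs on a surgery-based calendar: "Participants will be asked to wear the device beginning 1 week before surgery through postoperative week 6".

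**The concern.** A time to threshold is only as fine as the grid on which it is observed. Here each patient's grid is fine until discharge and coarse afterwards. Discharge happens after randomization and is partly a sign of recovery. Section 2.0 hypothesizes that the intervention speeds clinical recovery, so the grid may itself respond to treatment: an arm that leaves earlier moves to weekly scoring sooner.

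Chance could produce the same imbalance. Section 3.2 admits hip and knee, primary and revision surgery, section 3.3 plans 36 patients, and section 4.0 describes no stratification. If stay varies by procedure (plausible, but not documented), the arms can differ in stay without any treatment effect.

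Fatigue has a second exposure. Its threshold is half of the observed post-operative maximum, and that maximum can depend on how many daily scores were taken.

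At stake is the secondary aim in section 1.0: preliminary patient-centered outcomes, and their relation to flavanol intake and HMGB1-NFkB activation. Recorded times that depend on stay would blur both.

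**Working it through.** The plan gives no expected stay, resolution time or effect for these outcomes, so there is no figure of its own to reproduce. The schedule comes from section 4.0 and the endpoints from section 5.1. All other inputs below are assumptions.

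**1. Single patients (no distribution needed).** With discharge on day D, read weekly scoring as counted from discharge. The scoring days are then 1, 2, ..., D, D+7, D+14, and so on. Let pain become mild at day 2.5 in two patients.
- Discharge on day 4: the bracketing forms are days 2 and 3. First-form dating gives day 3; midpoint dating gives (2+3)/2 = 2.5.
- Discharge on day 2: the bracketing forms are days 2 and 2+7 = 9. First-form dating gives day 9; midpoint dating gives (2+9)/2 = 5.5.

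Equal true recovery is recorded 9 - 3 = 6 days apart under the first rule and 5.5 - 2.5 = 3 days apart under the second.

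**2. End of follow-up.** The last weekly form by day 42 falls on 2 + 5×7 = day 37 for a 2-day stay and 5 + 5×7 = day 40 for a 5-day stay.

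**3. Identical recovery, different stays.** Assume log-normal true times, median 3 days, log-SD 0.6, and one stay per arm. Simulated mean recorded times with first-form dating are 8.15, 7.48, 6.39 and 5.55 days for discharge on days 1, 2, 3 and 4. The range is 8.15 - 5.55 = 2.6 days of artefact. With midpoint dating it is about 0.7 day.

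**4. A true benefit.** Let recovery on active take 0.75 of the control time, with control median 3 days. The mean of a log-normal is median × exp(0.6²/2) = median × 1.197. The true mean benefit is therefore (3 - 2.25) × 1.197 = 0.90 day. Recorded benefit (control minus active):

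| Stay, active vs control (days) | First-form dating | Midpoint dating |
|---|---|---|
| 2 vs 3 | +0.4 | +0.6 |
| 1 vs 3 | -1.1 | +0.1 |

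At equal stays (2 vs 2), first-form dating records +1.4. Coarse dating alone therefore does not hide the benefit; the unequal stays do.

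**5. Stays that vary within arm.** Assume rounded normal stays (SD 0.8 day) with means 2 vs 4, independent of recovery, with unresolved patients set to day 42 and first-form dating.
- Medians 3.5 vs 4 days, true benefit about 0.6: the plan's schedule records -0.55. Counting weeks from surgery but keeping daily forms in hospital only still records -0.50. A grid common to all patients (days 1-7, then 14, 21, 28, 35 and 42) records +0.79.
- Medians 4 vs 4, no true difference: the plan's schedule records -1.19 against the shorter-stay arm; the common grid records -0.02.

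**6. Slower recovery.** In the model of step 4 with a control median of 7 days, moving from stays of 2 vs 2 to 2 vs 4 shifts the recorded difference by about 0.2 day. At 14 days, with identical recovery and stays of 2 vs 4, the shift is 0.06 day.

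**7. What a common grid leaves open.** At a control median of 7 days, the common grid with first-form dating records 2.7 days against a true 7 × 0.25 × 1.197 = 2.1, because the spacing widens after day 7. A dating rule or an interval-censored analysis is therefore still needed.

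**The case against.** The strongest reply is that the damaging figures stack assumptions that the documents do not supply: resolution mostly in the first week, stays that differ between arms, and dating to the first form at or after resolution. The protocol follows recovery for six weeks and its background describes protracted recovery, so a 3-day median to mild pain or function may be unrealistic. In the 1 vs 3 case the gap in stay (2 days) exceeds the recovery benefit (0.9 day) supposed to cause it. With mean stays of 2 vs 2.5 days (SD 0.8, rounded), the recorded benefit is +0.86 against a true +0.92, so almost nothing is lost. The outcomes are exploratory. With 36/2 = 18 per arm, the standard error of a difference in recorded times is about 1.2 to 1.4 days at a 3-day median, so a 0.9-day benefit would not be detectable on any grid.

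Most of this stands, and it limits the point. A reader might infer that the schedule will hide or reverse a benefit. The documents do not support that: reversal in the illustration depends on first-form dating, which section 5.1 neither states nor excludes, and midpoint dating leaves attenuation only. A reader might also infer that late resolution times follow the discharge day. Individual form days do shift with discharge, but group means barely move once recovery takes two weeks.

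The reply does not remove the mechanism. No passage supplies a common grid, a dating rule or an adjustment. Reading weekly as counted from surgery does not help either (step 5), because the switch at discharge remains.

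**Conclusion.** The concern holds in limited form. Recorded times to resolution from WOMAC and SRS depend on length of stay. If many patients resolve in about the first week and stays differ between arms, by treatment or by chance, an early benefit is attenuated. In the illustration a true 0.9 day becomes +0.4 or -1.1 with first-form dating, and +0.6 or +0.1 with midpoint dating. Where recovery takes about a week the effect of unequal stays is about 0.2 day; at two weeks it is negligible.

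These sizes rest on assumed stays and log-normal resolution times. The direction for early resolution follows from the schedule itself. The primary NFkB outcome, HMGB1 and the ActiGraph measures are unaffected, so this is a worthwhile, inexpensive improvement and no threat to the trial's main conclusion.

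**What to change.** In section 4.0, replace the questionnaire schedule with one counted from surgery and identical for all patients: WOMAC and SRS daily on post-operative days 1-7 wherever the patient is, then on days 14, 21, 28, 35 and 42. In sections 5.1 and 5.2, derive the times to resolution on that grid and analyse them as interval-censored data, or state midpoint dating. The dating rule matters even with the common grid (step 7). Changing only the anchor of the weekly forms is not enough.

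Cost: a change of wording, a few extra self-completed forms at home in the first week, slightly more patient burden and some missed forms. Daily home scores that were never collected cannot be recovered at analysis.
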